SLE is a chronic inflammatory disease that has renal effect in about half of patients. Lupus nephritis is a major risk factor for morbidity and mortality in patients with SLE, and in spite of strong anti-inflammatory and immunosuppressive therapies still ends in CKD or ESRD. (5)

Based on this observation, we aim to determine the effect of SGLT2i treatment in patients with glomerulonephritis secondary to SLE who either is diabetic or non-diabetic.

Aim of the work

This study aims to assess SGT2i role in regression of ongoing kidney and cardiac diseases among lupus nephritis patient either diabetic or non-diabetic under different immunosuppressive therapy.

Patients and methods

Technical design:

Study sitting: .1

Nephrology and renal transplant unit at urology and nephrology center in Mansoura University.

It will include 100 patients with lupus nephritis, Diagnosis of glomerulonephritis was performed by renal biopsy, and all of the renal biopsies were carried out at urology and nephrology center.

Patients with an estimated glomerular filtration rate (eGFR) >30 ml/min/1.73m2 will be randomized into two groups

- Study group will receive SGLT2i inhibitor as add on drug or replace
 another drug according to patient clinical situation, Dapagliflozin 10
 mg and 25 mg will be used once daily with or without food.
 - Control group will be maintained on placebo. •

The primary endpoint will be sustained decline in eGFR ≥50%, ESKD, or kidney or cardiovascular death

We will follow up all patients for 12 months and compare their results.

2. Inclusion criteria:

- Patients aged more than 16 year. .1
- Willing to sign informed consent. .2
- Diagnosis of SLE according to EULAR/ACR classification .3 criteria.
 - Renal biopsy showed lupus nephritis. .4
- Patient with eGFR > 30 ml/min/1.73m2 by cockcroft-gault .5 equation.

3. Exclusion criteria:

- Patients with eGFR <30 ml/min per 1.73 m2. .1
 - Current pregnancy or lactation. .2
- Medical history of chronic disease (CLD, cancer, severe .3 respiratory distress, gastrointestinal tract lesions).
- Patients refusing to participate in the study or lost follow up. .4
- Evidence of urinary obstruction of difficulty in voiding at .5 screening.

- Patients who are receiving high dose diuretics or combined .6 ACEI, ARBS.
- Patients who have frequent hypotensive episode or SBP .7 <100 mmHg.

Operational design:

Study Protocol:

Patients included in the study will treated with dapaglifilozin

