 initiated at a total daily dosage of 10 mg/kg per day.

Study design:

Type of the study: randomized controlled study.

The following data will be gathered and evaluated for all patients:

I-before intervention:

- Serum creatinine, Creatinine clearance. .1
- 24 hour urine protein, urine protein/creatinine ratio. .2
 - Urine analysis. .3
 - HBA1c. .4
 - HGB. .5
 - Uric acid and lipid profile. .6
 - Lupus serology. .7

II-after intervention: All patients will be evaluated monthly regarding:

- Serum creatinine, creatinine clearance. .1
- 24 hour proteinuria, protein/creatinine ratio. .2
- Fasting, random and postprandial glucose levels. .3
 - CNI trough level if used. .4
 - Urine analysis. .5
 - HGB level. .6
 - Uric acid, lipid profile. .7
 - Lupus serology. .8

Cardiovascular assessment: .9

ECCHO.

Atherosclerosis and vascular calcification incidence (NCCT model).

Regular measurement of blood pressure each visit.

Outcomes:

- Effect of dapagliflozin compared to placebo on eGFR. .1
- Effect of dapagliflozin compared to placebo on systolic/diastolic blood .2 pressure.
 - Effect of dapagliflozin compared to placebo on body weight. .3
- Safety of dapagliflozin vs. placebo the number of hypoglycemia .4 episodes between groups and serious adverse events.

Statistical Analysis:

Qualitative data were displayed in cross tabulations, and quantitative data were described in terms of arithmetic mean ± SD. Bivariate techniques were used for initial evaluation of contrasts. Thus, the chi-square and Fisher's exact tests were used for comparisons of frequencies of qualitative variables; the Mann-Whitney test and the unpaired t-test were used for comparisons of means of two quantitative variables. A p-value <0.05 was considered significant. Graft and patient survival rates were assessed using the Kaplan-Meier method. All analyses were carried out using the computer package SPSS for windows, release 16 SPSS Inc. Chicago, III, USA.

Administrative design •

Informed consent will be obtained from all subjects and the approval will be obtained from institutional review board (IRB) in Faculty of Medicine, Mansoura University. There is no funding.

Research question

The main research question is: Does use of SGLT2i will show superiority over conventional lines of treatment of lupus nephritis patient as regard efficacy and safety.

Rationale and justification

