Statistical Analysis Plan

Document Control

Title: Statistical Analysis Plan for the Study of SGLT2 Inhibitors in Lupus Nephritis Patients

Protocol ID: [NCT05748925] Version: 1.0 Date: [11/3/2024] Principal Investigator: [[name]] Statistician: [[name]] Approval Signatures: Principal Investigator: [name] Statistician: [name]

Table of Contents

- 1. Introduction
- 2. Study Design
- 3. Study Objectives
- 4. Endpoints
- 5. Sample Size Justification
- 6. Statistical Methods
- 7. Handling of Missing Data
- 8. Interim Analysis
- 9. Safety Analysis
- 10. Data Quality and Management
- 11. Software
- 12. Appendices

1. Introduction

• **Purpose of the SAP**: This document outlines the statistical approach for analyzing data from the clinical trial studying the effects of SGLT2 inhibitors on renal, cardiovascular, and hematological outcomes in lupus nephritis patients.

2. Study Design

Design: Randomized, double-blind, placebo-controlled clinical trial.

Study Duration: Conducted from September 2022 to November 2023

Randomization: Patients were randomly assigned to either dapagliflozin (10 mg once daily) or placebo groups using computer-generated random tables in a 1:1 ratio stratified by age and gender.

Blinding: The study was double-blinded, and all trial staff and participants remained unaware of individual treatment assignments until study completion.

3. Study Objectives

Primary Objective: To evaluate the impact of SGLT2 inhibitors on renal, cardiovascular, and hematological parameters in lupus nephritis patients.

Secondary Objective: To explore changes in body weight, BMI, and other echocardiographic and iron profile parameters over 12 months.

4. Endpoints

Primary Endpoints

Renal Function: Serum creatinine, eGFR, and 24-hour urine protein

Cardiovascular Health: BNP levels and coronary calcification via NCCT

Hematological Parameters: Hemoglobin and erythropoietin levels

Hepcidin Level: Measured before and after intervention

Secondary Endpoints

Body Weight and BMI: Assessed at baseline and follow-up visits.

Echocardiographic Findings: Assessed pre- and post-intervention.

Iron Profile: Serum ferritin and TSAT

5. Sample Size Justification

Calculation: A sample size of 100 patients was targeted, accounting for potential dropouts, to provide sufficient power (80%) at a significance level of 0.05 to detect differences between the two groups.

6. Statistical Methods

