
General Considerations

Significance Level: A two-sided alpha level of 0.05 will be used for all primary analyses.

Analysis Populations:

Intent-to-Treat (ITT): All randomized patients will be analyzed according to their assigned group.

Per-Protocol (PP): Only patients completing the study without major protocol violations.

Primary Endpoint Analysis

Renal Outcomes: ANOVA for repeated measures for serum creatinine and eGFR if normally distributed, and the Friedman test for non-normally distributed data. Post-hoc tests using Bonferroni correction.

Cardiovascular Outcomes: Mann-Whitney U test for BNP levels and coronary calcification between groups.

Hematological Outcomes: Paired t-test for hemoglobin and erythropoietin levels if data is normally distributed; otherwise, Wilcoxon signed-rank test.

Secondary Endpoint Analysis

Body Weight and BMI: Compared over time using ANOVA for repeated measures.

Echocardiographic Parameters: Analyzed with paired t-tests, adjusted with Bonferroni correction.

Iron Profile: Analyzed pre- and post-intervention using ANOVA or Kruskal-Wallis for non-normally distributed variables.

Categorical Variables

Chi-Square Test: For between-group comparisons of categorical data (e.g., presence of diabetes, hypertension).

7. Handling of Missing Data

Imputation: Last observation carried forward (LOCF) for data missing at random; multiple imputation for extensive missing data.

Sensitivity Analysis: Conducted to evaluate the robustness of primary endpoint findings against different missing data assumptions.

8. Interim Analysis

Timing: An interim analysis is planned at the halfway point (6 months).

Stopping Rules: An O'Brien-Fleming approach will be applied to adjust the significance threshold for interim testing, allowing for an earlier stop for efficacy or safety concerns.

9. Safety Analysis

Adverse Events (AEs): Summarized by type, frequency, and severity. Fisher's exact test will be used to compare AE rates between groups.

Specific Safety Parameters: Monitoring for hypotension, electrolyte imbalances, and kidney function.

10. Data Quality and Management

Data Quality Measures: Includes data verification, regular audits, and query resolution.

Database Lock: Data will be locked and verified prior to the final analysis.

11. Software

Statistical Software: All analyses will be conducted using SPSS (Version 25).

12. Appendices

	Control group. (n= 41)	Study group. (n= 38)	P value

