Age (years) Mean ± SD	36.6 ± 9.6	38±9.8	0.8
Sex No. (%) - Male - Female	7 (17.1%) 34 (82.9%)	4 (10.5%) 34 (89.5%)	0.5
Body weight (Kg) mean ± SD	78.9 ± 14	90 ± 15	0.5
Body mass index (Kg/m ²) mean ± SD	30.6 ± 10.5	33±5.7	0.6
Hypertension No. (%)	37 (90.2%)	38 (100%)	0.1
Diabetes No. (%)	7 (17.1%)	11 (28.9%)	0.2

Table (1): Demographics and associated medical disorders:

(Student T test or Mann-Whitney) for continuous data, and chi-square test for categorical data. Continuous data are expressed as mean (SD) or median (minimum – maximum). Categorical data are expressed as number (percentage), Level of significance < 0.05.

Table (2): SLE characteristics:

	Control group. (n= 41)	Study group. (n= 38)	P value
Disease duration (years) Median (min, max)	6 (1, 20)	7(1,19)	0.3

Lupus nephritis class No.			
(%)			
- Class I	1 (2.4%)	1 (2.6%)	
- Class II	2 (4.9%)	7 (18.4%)	0.1
- Class III	11 (26.8%)	8 (21.1%)	0.1
- Class IV	26 (36.4%)	16 (42.1%)	
- Class V	5 (2.4%)	1 (13.2%)	
- Class VI	0 (0%)	1 (2.6%)	
Activity index Median	6 (0, 10)	6 (0, 21)	0.8
(min, max)	0 (0, 19)	0 (0, 21)	0.8
Chronicity index Median	2(0, 8)	5 (0, 14)	0.2
(min, max)	2 (0, 8)	5 (0, 14)	0.2
Anti- phospholipid No.	6 (14 6%)	3 (7.0%)	0.4
(%)	0 (14.070)	5 (7.970)	0.4
Immunosuppressive			
medications No. (%)			
- Steroid + MMF	27 (65.9%)	18 (47 4%)	
- Steroid + CNI	5 (12.2 %)	4(10.5%)	0.2
- Steroid + CNI + MMF	2 (4.9 %)	1 (2 6%)	0.2
- Steroid + Azathioprine	7 (17.1%)	14(36.8%)	
- Steroid	0 (0%)	1 (2 6%)	
		1 (2.070)	
Cyclophosphamide No.	7 (17 1%)	5 (13.2%)	0.7
(%)	(1,11,0)		
Other medications No. (%)			
- Aspirin	15 (36.6%)	18 (34.4%)	0.3
- Statins	30 (73.2%)	24 (63.2%)	0.4
- Allopurinol	10 (24.4%)	14 (36.8%)	0.3
- ACEI/ARBS	26 (63.4%)	27(71.1%)	0.4
- Diuretics	14 (34.1%)	16 (32.1%)	0.3

MMF: mycophenolate mofetil; CNI: calcineurin inhibitors; ACEI/ARBS: angiotensin converting enzyme inhibitors/angiotensin receptor blockers; (Student T test or Mann-Whitney) for continuous data, and chi-square test for categorical data. Continuous data are expressed as mean (SD) or median (minimum – maximum). Categorical data are expressed as number (percentage).; Level of significance < 0.05.

	Control group. (n= 41)	Study group. (n= 38)	P value
Consumed C3 & C4 No. (%)	5 (12.2%)	2 (5.3%)	0.4

S. creatinine (mg/dL) Median (min, max)	0.8 (0.4, 2.7)	0.8 (0.4, 2.6)	0.8
24- hour urinary protein (g/24 hours) mean ± SD	0.4 (0.06-3.6)	0.6 (0.07-3)	0.3
eGFR (ml/min/m ²) mean ± SD	114 ± 51	128 ± 59.7	0.6

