BNP: Brain natriuretic peptide; EF: Ejection fraction; LAD: Left atrial dimension; ESV: End-systolic volume; EDV: End diastolic volume; (Student T test or Mann-Whitney) for continuous data, and chi-square test for categorical data. Continuous data are expressed as mean (SD) or median (minimum – maximum). Categorical data are expressed as number (percentage).; Level of significance < 0.05.

Table (6): Comparison between study and control groups as regard effect of intervention on
 disease activity and renal affection at different time points

	Grouping	Baseline	3 months	6 months	9 months	12 months	P value*
Consumed C3 & C4	Control	5 (12.2%)	5 (12.2%)	4 (9.8%)	6 (14.6%)	10 (24.4%)	0.1
No. (%)	Study	2 (5.3%)	5 (13.2%)	2 (5.3%)	6 (15.8%)	6 (15.8%)	0.1
	P value**	0.4	0.9	0.3	1	0.4	
S. creatinine (mg/dL)	Control	0.8 (0.4, 2.7)	0.9 (0.4, 3.1)	0.9 (0.3- 3.1)	0.9 (0.6, 4)	0.9 (0.6, 5)	0.1
Median (min, max)	Study	0.8 (0.4, 2.6)	0.9 (0.6, 2.6)	0.9 (0.5, 3.1)	1 (0.5, 4.2) a	0.9 (0.5, 5)	0.01
	P value**	0.8	0.8	1	0.5	0.8	
eGFR (ml/min/m²) Mean ± SD	Control	114±51	104±45 a	107±53.8	99±47 a	100.3±44.5 a	0.003
	Study	128±59.7	115±47 A	118±50 A	109±44.5 a, c	115.7±48 a	0.001
	P value**	0.6	0.9	0.8	0.2	0.9	
	Control	0.4(0.06- 3.6)	0.6 (0.03-5)	0.6 (0.03- 7)	0.6 (0.02, 5)	0.5 (0.02 , 8)	0.06
24- hour urinary protein (g/24 hours) Median (min, max)	Study	0.6 (0.07-3)	0.7 (0.01-4)	0.8 (0.02, 4.8)	0.6 (0.05, 4.7)	0.5 (0.02 , 4)	0.07
	P value**	0.3	0.9	0.8	0.6	0.6	
Albumin (g/dL)	Control	3.7±0.4	3.7±0.4	3.6±0.4	3.8±0.4 c	3.9±0.3 a, b, c	0.001
iviean ± SD.	Study	3.7±0.3	3.7±0.5	3.7±0.3	3.8±0.3 c	3.9±0.8 a, c	0.04
	P value**	0.4	0.9	0.1	0.7	0.8	

(*) Within group analysis (repeated measure ANOVA).

(**) Between group analysis (Student T test or Mann-Whitney) for continuous data, and chi-square test for categorical data. Post-hoc analysis;

(a) significance against baseline <0.05; (b) significance against 3 months level <0.05, (c) significance against 6 months level <0.05, (d)

significance against 9 months level <0.05. Continuous data are expressed as mean (SD) or median (minimum – maximum). Categorical data are expressed as number (percentage).

Table (7): effect of intervention on hematological findings between both groups at different time points:

	Grouping	Baseline	3 months	6 months	9 months	12 months	P value*
Haemoglobin (g/dL) Mean ± SD	Control	11.9±1.9	12.2±1.9	11.8±2.5	12±1.9	12.2±1.9	0.08
	Study	11.8±1.8	12.3±1.7	12±2.5	11.9±2.2	12±2	0.06

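### Several printed between-arm p-values do not fit the printed data, most clearly baseline body weight (0.5 printed, 0.001 recomputed), and eGFR is compared between arms without adjustment for a 14-unit baseline gap

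*Protocol*

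**What the plan says.** **Endpoint and analysis.** SAP 4 lists "Renal Function: Serum creatinine, eGFR, and 24-hour urine protein" among the primary endpoints. SAP 6 names "ANOVA for repeated measures for serum creatinine and eGFR if normally distributed", with a Friedman test otherwise. It gives no between-arm contrast and no baseline covariate.

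**Appended results.** The footnote to Table 6 ties the repeated-measures ANOVA to one use: "Within group analysis (repeated measure ANOVA"). The arms are compared separately at each visit by a t-test or a Mann-Whitney test on the raw values. The footnotes to Tables 1 to 4 offer the same two tests. None says which test produced which row.

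**Weight.** The Table 1 row "Body weight (Kg) mean ± SD" shows 78.9 ± 14 against 90 ± 15 with p=0.5. Weight is a protocol outcome and a SAP secondary endpoint.

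**Definition of eGFR.** The protocol names an equation once, in inclusion criterion 5: "Patient with eGFR > 30 ml/min/1.73m2 by cockcroft-gault". It also collects "Serum creatinine, Creatinine clearance" and, at the monthly visits, "24 hour proteinuria, protein/creatinine ratio". No section states the equation, weight input or indexing for endpoint eGFR. The row label in Table 6 is "eGFR (ml/min/m²) Mean ± SD", a different unit from the one in the inclusion criterion.

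**The concern.** An 11 kg gap between arms of about 40 patients, with SDs near 15 kg, cannot sit beside p=0.5. If the means and SDs are right, a significant baseline imbalance in an outcome variable is presented as balance. If the p-value is right, the descriptive figures are wrong. In neither case can a reader rely on the row.

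For eGFR, a SAP primary endpoint, there are two separate questions. One is whether the printed between-arm p-values can be trusted. The other is what a raw comparison at 12 months measures when the study arm already started 14 units higher. Without baseline in the comparison, the 12-month gap mixes starting level with treatment effect, and the interval around it is wider than it need be.

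**Working it through.** **Inputs.** Means and SDs come from Tables 1, 3, 4, 5 and 6, with n=41 control and n=38 study. The same denominators apply at 12 months in Table 6: 10/41 = 24.4% and 6/38 = 15.8% for consumed complement.

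**Method.** Pooled t-test on 77 df: SE = SDp × √(1/41 + 1/38), where SDp² = (40·SD₁² + 37·SD₂²)/77.

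**Check of the method on other rows.** End-diastolic volume in Table 5 (98 ± 35.7 vs 111.5 ± 31.6) gives 0.08; printed 0.08. Hepcidin in Table 4 (198 ± 74 vs 182 ± 76) gives 0.35; printed 0.3. So some rows do reproduce.

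**Body weight.**
- SDp = 14.49, SE = 3.26, difference = 90 − 78.9 = 11.1.
- t = 11.1/3.26 = 3.40, p = 0.0011 (Welch 0.0011), 95% CI 4.6 to 17.6.
- With every printed figure rounded in the least favourable direction, p = 0.0025.
- Mann-Whitney was simulated on samples forced to the printed means and SDs. The largest p was 0.013 with normal, lognormal and gamma shapes in any pairing (27,000 sets), and 0.078 after adding strong left and right skew (37,500 sets).
- A t-test p of 0.5 would need a difference of about 2.2 kg or an SD of about 73 kg.

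**BMI, control arm.** The coefficients of variation are 10.5/30.6 = 0.343 for BMI and 14/78.9 = 0.177 for weight. With lognormal variables, and weight and height uncorrelated, var(log height) = [ln(1 + 0.343²) − ln(1 + 0.177²)]/4 ≈ 0.020. That is a height SD of about 24 cm, with 95% of heights between 1.24 and 2.16 m. A weight-height correlation of 0.3 raises the SD to 29 cm. The study arm needs only 4 to 10 cm.

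**eGFR by visit.**

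| Month | Control | Study | Difference | t-test p | Printed p |
|---|---|---|---|---|---|
| 0 | 114 ± 51 | 128 ± 59.7 | 14 | 0.26 | 0.6 |
| 3 | 104 ± 45 | 115 ± 47 | 11 | 0.29 | 0.9 |
| 6 | 107 ± 53.8 | 118 ± 50 | 11 | 0.35 | 0.8 |
| 9 | 99 ± 47 | 109 ± 44.5 | 10 | 0.34 | 0.2 |
| 12 | 100.3 ± 44.5 | 115.7 ± 48 | 15.4 | 0.14 | 0.9 |

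At 12 months SE = 10.4, so a t-test p of 0.9 would need a gap of about 1.3. In the Mann-Whitney simulations:
- **Month 12:** p ≥ 0.85 occurred in at most 0.03% of sets for any pairing of normal, lognormal and gamma shapes. With strong skew added it reached 16% in one pairing (control left-skewed, study strongly right-skewed) and at most 1.4% in the other 24.
- **Month 3:** the corresponding maxima are 2.3% and 41%, so that value is doubtful rather than impossible.
- **Months 0 and 6:** with a normal control arm and a lognormal study arm, the 5–95% ranges of p are 0.32–0.79 and 0.32–0.84, so 0.6 and 0.8 are reachable.

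**Other rows, t-test against printed.** Age 0.52 vs 0.8; cholesterol 0.19 vs 0.5; sodium 0.15 vs 0.5; uric acid 0.49 vs 0.2; MCV 0.21 vs 0.9; MCH 0.17 vs 0.9. Sodium is the weakest of these. Its means are printed as whole numbers (137 and 136), so the true difference could be anywhere from 0 to 2, and p=0.5 needs only about 0.47.

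**Baseline adjustment at 12 months.** Adjusted difference = 15.4 − β × 14, with β = r × 46.2/55.4 (pooled SDs at 12 months and baseline). The correlation r between baseline and 12-month eGFR is not given and is assumed.

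| Assumed r | β | Difference | 95% CI |
|---|---|---|---|
| Raw | – | 15.4 | −5.3 to 36.1 |
| 0.5 | 0.417 | 9.6 | −8.7 to 27.8 |
| 0.7 | 0.584 | 7.2 | −7.8 to 22.2 |
| 0.9 | 0.751 | 4.9 | −4.3 to 14.0 |

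The gap shrinks by 38% to 68% and the interval narrows by 12% to 56%.

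**The case against.** **The eGFR p-values could be Mann-Whitney results.** The footnote allows that test, and it can explain the baseline and 6-month values. At 12 months it cannot be excluded outright, so a reader who infers that 0.9 is impossible goes too far. A test on change from baseline would give about 0.90 at r = 0.5 (mean changes −13.7 and −12.3, difference 1.4). The footnote describes no such test, however, and the printed baseline value of 0.6 cannot come from one. Moving from 0.9 to 0.14 does not change significance at 0.05. All of this stands, and it is a further reason to name the test for each row.

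**An unadjusted comparison in a randomised trial is valid.** This is correct. The baseline eGFR gap has p=0.26 and a 95% CI of −11 to 39, so it is compatible with chance and does not show failed randomisation. Every adjusted interval includes zero, as the raw one does. Repeated-measures ANOVA could carry an arm-by-visit term, but SAP 6 does not specify one and Table 6 does not report one. What remains is a loss of precision and of interpretability.

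**The weight imbalance might be thought to have distorted eGFR through Cockcroft-Gault.** A reader might infer this because that equation is proportional to body weight. The documents do not support it. They name the equation for eligibility only, and measured clearance remains possible because 24-hour urine is collected. The table unit may simply have lost its 1.73. Mismatched p-values in unrelated rows such as MCV also mean that the eGFR mismatch is no evidence of an equation problem.

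**The BMI calculation rests on a distributional model.** It may point to an error in the BMI entry and not in weight. That stands: it justifies a source check but does not identify which figure is wrong.

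**Conclusion.** The point holds in two parts.

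First, the weight p-value of 0.5 is incompatible with its own row under either permitted test: 11.1 kg, 95% CI 4.6 to 17.6, p=0.001. Either a significant baseline imbalance is shown as balance or the printed figures are wrong, and the documents do not say which. The 12-month eGFR p of 0.9 is very unlikely given the printed means and SDs. The mismatch extends to other rows of Tables 1, 3, 4 and 6, some of which Mann-Whitney or rounding could explain. These results assume that the printed means, SDs and group sizes are correct.

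Second, the between-arm eGFR comparison leaves out baseline values that are already held. The size of the gain depends on the assumed correlation.

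No between-arm eGFR conclusion is shown to reverse. The missing equation and the inconsistent unit need clarifying but are minor.

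**What to change.** 1. Check the weight and BMI rows of Table 1 against source data and correct whichever figure is wrong. Re-derive all between-arm p-values in Tables 1, 3, 4 and 6, and name the test for each row. Checking only weight and eGFR would leave likely errors elsewhere.
2. Make the between-arm eGFR comparison adjusted for baseline eGFR. Use ANCOVA at 12 months, or one repeated-measures model with arm, visit, arm-by-visit and baseline eGFR, and report the difference with its 95% CI.
3. As a minor clarification in SAP 4 and 6, state the eGFR equation (or measured clearance), the weight input and one unit label. A sensitivity analysis with a weight-free creatinine equation is optional, and relevant only if Cockcroft-Gault was used for the endpoint. The eligibility rule is not affected.

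The cost is a source check of two rows, a rerun of simple tests and one extra model, all on data already held. Because the SAP already contains the 12-month results, the adjusted comparison and any added equation must be labelled post hoc and cannot be confirmatory.

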End diastolic volume; Chi square test; Student t- test; Man, Whitney test; Level of significance < 0.05.

Table (10): Comparison between both groups as regard post intervention side effects

	Control group. (n= 41)	Study group. (n=38)	P value
AKI episodes No. (%)			
- No	38 (92.7%)	31 (81.6%) 5 (13.2%)	0.17
- once	1 (2.4%) 2 (4.9%)	2 (5.3%)	
- twice			
UTI No. (%)			
- No	35 (85.4%) 4 (9.8%)	31 (81.6%) 5 (13.2%)	0.8
- once	2 (4.9%)	2 (5.3%)	
- more than once			
Gynecological infection No. (%)	1 (2.4%)	2 (5.3%)	0.6
Viral infection No. (%)	1(2.4%)	1 (2.6%)	1
MMF intolerance No. (%)	1 (2.5%)	2 (5.3%)	0.6
Renal biopsy No. (%)	2 (4.9%)	1 (2.6%)	0.6
Increase steroid dose No. (%)	7 (17.1%)	4 (10.5%)	1

UTI: urinary tract infection episodes; AKI: acute kidney injury; chi-square test for categorical data. Categorical data are expressed as number (percentage).; Level of significance < 0.05.

figure1: flow chart of participating populations

Figure (2) shows difference between individual which had improved eGFR or not as regard to their basal eGFR in total cohort, which found that improving eGFR had been occurred in patients with lower eGFR (107±50 vs 137±58 ml/min/m²

Figure (3) show no significant difference between the drug and placebo groups (p=0.857). as regard incidence of anemia before intervention, the drug group has 23 anemic participants (60.5%) versus 24 participants (58.5%) in the placebo group, while post intervention, In the anemia category, the drug group has 16 participants (42.1%), while the placebo group has 22 participants (53.7%) with non-significant differences (p = 0.3)

Figure (4) differences in body weight between both groups at different time points:

Glossary of Terms and Abbreviations

AA	Amino Acids
ABIN	A20 Binding Inhibitor Of NF-Kb
ACE	Angiotensin-Converting Enzyme Inhibitors
ACR	American College of Rheumatology
AKI	Acute Kidney Injury
ALCAM	Activated Leucocyte Adhesion Molecule
ALP	Alkaline Phosphatase
AMP	Adenosine Monophosphate
АМРК	Amp-Activated Protein Kinase
ANA	Antinuclear Antibodies
ANG II	Angiotensin 2
ANOVA	Analysis Of Variance
ANTI-DSDNA	Anti Double Stranded Deoxyribonucleic Acid
	Antibodies
ANTI-SM	Anti-Smith Antibodies
APLS	Antiphospholipid Syndrome
ARBS	Angiotensin 2 Receptor Blockers
ATN	Acute Tubular Necrosis
ATP	Adenosine Triphosphate
BAFF	B-Cell-Activating Factor
BLISS	B Lymphocyte Stimulator Inhibitor Belimumab
	Plus Standard Therapy
BMI	Body Mass Index
BNP	Brain Natriuretic Peptide
BP	Blood Pressure

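### Exclusion criterion 4 lists loss to follow-up, which is known only after randomisation; applied as written it conflicts with the SAP's ITT set

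*Protocol*

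**What the plan says.** The protocol's exclusion criteria list, as item 4, "Patients refusing to participate in the study or lost follow up". No time point is attached to it. On follow-up, the protocol's patients and methods section says: "We will follow up all patients for 12 months and compare their results". The protocol defines no analysis population and no rule for missing data, so item 4 is its only statement about patients who are lost.

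SAP section 6 defines the ITT set: "All randomized patients will be analyzed according to their assigned group". It also defines a per-protocol set of completers without major violations, but does not say which set is primary. Section 7 provides LOCF, multiple imputation and a sensitivity analysis. Nothing in the SAP withdraws or explains criterion 4.

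On numbers, the protocol says "It will include 100 patients with lupus nephritis" and SAP section 5 says "A sample size of 100 patients was targeted, accounting for potential dropouts". The tables in SAP section 12 are headed 41 control and 38 study patients wherever a group size is printed.

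**The concern.** Eligibility criteria should rest on facts known before randomisation. A patient lost during the 12 months has already been allocated. If that patient is then treated as excluded, the sample is selected on something that happened after allocation and that treatment may have influenced. Such a rule and an ITT set of all randomised patients cannot both be followed.

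If the rule is followed, the ITT set shrinks towards the completers and the comparison loses the protection of randomisation. The SAP's missing-data methods would no longer cover the patients who left, although they would still apply to missed visits and assays in those who stayed. The rule also sits badly with the protocol's Kaplan-Meier method, which censors lost patients and does not delete them.

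The protocol's primary endpoint is a sustained eGFR decline of at least 50%, ESKD, or kidney or cardiovascular death. Its safety outcomes are hypoglycaemia and serious adverse events. Patients heading towards such events, or tolerating treatment poorly, may plausibly be among those who stop attending, and not equally in both arms.

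**Working it through.** **1. The plan's own figure.** The SAP targets 100 patients "to provide sufficient power (80%) at a significance level of 0.05 to detect differences between the two groups", and its alpha is two-sided. It gives no endpoint, effect size, SD or dropout rate, so the 100 can be neither reproduced nor refuted. Solving for the standardised difference by the normal approximation, d = (1.960 + 0.842) × √(1/n₁ + 1/n₂):

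- 50 and 50: 2.802 × 0.2000 = 0.56
- 41 and 38: 2.802 × 0.2252 = 0.63

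Power at d = 0.56 falls from 80% to 70%. This follows from having 79 rather than 100, whatever the reason, so it says nothing about removal.

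**2. Denominators in the SAP tables.** Tables 1, 2, 4, 5 and 10 and the baseline laboratory table print 41 and 38. Tables 6 to 9 print no group sizes, but some counts with percentages allow them to be recovered:

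- Table 6, low C3 and C4, control: 5/41 = 12.2% at baseline, 10/41 = 24.4% at 12 months. Study: 2/38 = 5.3% and 6/38 = 15.8%. The 3-, 6- and 9-month cells fit the same denominators.
- Table 9, no coronary calcification at 12 months: 40/41 = 97.6% and 27/38 = 71.1%.
- Figure 3 text, anaemia after intervention: 22/41 = 53.7% and 16/38 = 42.1%.

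There are exceptions. In Table 10, control MMF intolerance is 1 (2.5%), which fits 1/40; 1/41 is 2.4%. Some Table 2 percentages do not match their counts at all (study-arm aspirin is 18 (34.4%), but 18/38 = 47.4%). For creatinine, eGFR, proteinuria and haemoglobin at follow-up visits, no denominator can be recovered.

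**3. Size, as an illustration.** Table 10, titled "Comparison between both groups as regard post intervention side effects", gives counts by arm. AKI at least once was 5 + 2 = 7 of 38 in the study arm and 1 + 2 = 3 of 41 in control. The difference is 18.4% − 7.3% = +11.1 points.

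The number randomised is not in the available text, so it is an assumption here. With N_S and N_C randomised, and m_S and m_C of them removed:

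- lowest difference = 7/N_S − (3 + m_C)/N_C
- highest difference = (7 + m_S)/N_S − 3/N_C

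| Assumed randomised (control/study) | Removed (control/study) | Lowest | Highest |
|---|---|---|---|
| 50/50 | 9/12 | 7/50 − 12/50 = −10 points | 19/50 − 3/50 = +32 points |
| 45/45 | 4/7 | 7/45 − 7/45 = 0 | 14/45 − 3/45 = +24 points |
| 41/38 | 0/0 | +11.1 points | +11.1 points |

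At 50/50 the span is 9/50 + 12/50 = 42 points. These are extreme bounds, in which either all or none of the removed patients in an arm had AKI. They measure how much is unknown and are not an estimate.

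**The case against.** Three arguments run the other way.

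First, criterion 4 may concern patients already lost to clinic follow-up before enrolment. It is paired with refusal to participate, and the next criterion is tied to screening. This reading is possible, but the text does not state it: the next item carries a time point and item 4 does not. If it was meant, the wording still needs correcting.

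Second, the SAP already names an ITT set of all randomised patients and has missing-data rules. That stands, and it is why this is a conflict between documents rather than a missing plan. It does not settle which text governs, because the SAP neither withdraws the criterion nor names the primary set.

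Third, a reader might infer from 79 against 100, with steady denominators, that 21 randomised patients were in fact deleted. The documents do not support that. Recruiting only 79 would explain the shortfall, and complete follow-up or the SAP's own LOCF would explain the steady denominators. The participant flow chart that would decide it is not shown in the text available, which is not a fault in the plan.

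**Conclusion.** The concern holds as a contradiction on the face of the documents: a stated exclusion rule that, applied as written, removes randomised patients and conflicts with the ITT definition. This does not depend on how the 79 arose, and it leaves open who is to be analysed, so it needs to be resolved.

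Whether anyone was removed is not established. The tables are consistent with removal and no more. The −10 to +32 point range for AKI requires that 100 were randomised exactly 50/50 and that all 21 absent patients were removed. It narrows to 0 to +24 at 45/45. If 79 were randomised, it vanishes and only ordinary sampling error remains.

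A reader might also infer that the rule makes dapagliflozin look safer or more effective than it was. The direction is in fact unknown: the bounds lie on both sides of the observed difference, and losing sicker control patients would work against the drug.

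**What to change.** Strike the loss-to-follow-up wording from the exclusion criteria, or limit it explicitly to non-attendance before screening. Refusal of consent can stay. State in the SAP that criterion 4 removes no randomised patient, and name ITT (all randomised) as the primary set.

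The SAP gives November 2023 as the end of the study, so the wording change cannot alter conduct and the practical remedy lies in analysis and reporting. Report the numbers randomised, lost (with reasons) and analysed, by arm and visit. If any randomised patients were removed, restore them with whatever data they have, analyse them under the SAP's missing-data and sensitivity provisions, and label the 41/38 set a completer analysis. If exactly 79 were randomised and none removed, one sentence and the flow numbers close the point.

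The cost is small if nobody was removed. Otherwise it is some record work and re-analysis, with denominators that may vary by visit.
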